Now reads: Regardless of causality, SAEs and serious pretreatment events (as defined in Section 10.1) must be reported (see Section 10.3 for the period of observation) by the investigator to the Millennium **Department of Pharmacovigilance or designee** (contact information provided below). This should be done by faxing the SAE Form within 24 hours after becoming aware of the event. The SAE Form, created specifically by Millennium, will be provided to each clinical study site. A sample of the SAE Form may be found in the Study Manual. Follow-up information on the SAE or serious pretreatment event may be requested by **the Millennium Department of Pharmacovigilance or designee**. SAE report information must be consistent with the data provided on the eCRF.

Sections that also contain this change are:

- Section [10.3, Monitoring of Adverse Events and Period of Observation](#)
 - Section [10.4, Procedures for Reporting Drug Exposure During Pregnancy and Birth Events](#)
 - Section [11.11, Product Complaints and Medication Errors](#)
-

Purpose: Update contact information for reporting SAEs

The primary change occurs in Section 10.2, [Procedures for Recording and Reporting Adverse Events and Serious Adverse Events](#):

Formerly read:	For SAE and Pregnancy Reporting Contact Information, please refer to Section 15.5.
Now reads:	SAE Reporting Contact Information  A large black rectangular redaction box covers the contact information. The letters 'CCI' are printed in red at the top left corner of the redacted area.

Section 15.5, SAE and Pregnancy Reporting Contact Information, has been deleted.

Purpose: Correct errors in Background and Study Rationale text and in-text references

The primary change occurs in Section 1.4.1, [Treatment Options in CTCL](#), and Section 1.4.2.1, [Bexarotene](#):

Formerly read: 1.4.1 Treatment Options in CTCL

There is no universally accepted single standard of care across first, second, and advanced lines of treatment of CTCL. Single-agent therapy has been used, including retinoids, interferons, HDAC inhibitors, and chemotherapy; these therapies include methotrexate, bexarotene, glucocorticoids, cyclophosphamide, cisplatin, etoposide, bleomycin, doxorubicin, vincristine, and vinblastine.⁽²⁷⁾ Single-agent therapy can yield complete response rates up to 30%, but remissions are generally of short duration. Chemotherapy combined with other agents may induce remissions of pcALCL. More potent chemotherapy is complicated by immune deficiency, and infectious complications. Both methotrexate and bexarotene are approved by the FDA and remain the most widely used treatments for CTCL across the diagnoses.⁽⁵⁾

...

A second HDACi, romidepsin, is an intravenously administered bicyclic peptide that inhibits classes I and II HDACs with activity in not only CTCL, but also peripheral T-cell lymphoma (PTCL). A single-arm, open-label, multicenter, pivotal, phase 2 study of romidepsin for the treatment of refractory CTCL (stages IB–IVA) was recently completed. After 6 cycles of treatment, a response rate (RR) of 42% was observed in 72-evaluable patients

(including 6 clinical CRs), and pruritus improved in 48%. Median time to response was ~~1.9~~ months.⁽²¹⁾ Romidepsin was granted approval by the FDA for treatment of patients with CTCL.^(21, 35)

Chemotherapy is reserved for relapsed and refractory disease and yields moderate to high response rates; however, response durations are short. Agents with notable activity include gemcitabine and liposomal doxorubicin. In a phase 2 study, gemcitabine showed a response rate of 53% and a CR rate of 22%. In a retrospective analysis of pegylated liposomal doxorubicin, the response rate was approximately 85% (30 out of 34 patients) and approximately 43% had CR.^(22, 23, 24)

1.4.2 Choice of Comparator

1.4.2.1 Bexarotene

Bexarotene (Targretin[®]) is approved in the United States and European Union for the treatment of patients who are refractory to at least 1 prior systemic therapy for cutaneous T-cell lymphoma. In clinical trials, bexarotene was administered for up to 97 weeks. In patients with advanced CTCL, 49% of patients achieved an objective response (complete and partial responses) to treatment with any dose of bexarotene. Patient response rates were 45% at a dose of 300 mg/m²/day PO and 55% at doses > 300 mg/m²/day PO. Responses were seen in patients with erythrodermic CTCL (mycosis fungoides) and Sézary syndrome. Median time to best response was 180 days and these responses were durable for a median of ~~159~~ days at bexarotene doses of 300 mg/m²/day PO. Median time to response was shorter and the duration of response was longer with doses > 300 mg/m²/day PO but the incidence of side effects increased substantially at the higher doses.⁽³⁶⁾

Now
reads:

1.4.1 Treatment Option in CTCL

There is no universally accepted single standard of care across first, second, and advanced lines of treatment of CTCL. Single-agent therapy has been used, including retinoids, interferons, HDAC inhibitors, and chemotherapy; these therapies include methotrexate, bexarotene, glucocorticoids, cyclophosphamide, cisplatin, etoposide, bleomycin, doxorubicin, vincristine, and vinblastine.⁽²⁶⁾ Single-agent therapy can yield complete response rates up to 30%, but remissions are generally of short duration. Chemotherapy combined with other agents may induce remissions of pcALCL. More potent chemotherapy is complicated by immune deficiency, and infectious complications. Both methotrexate and bexarotene are approved by the FDA and **are** widely used treatments for CTCL across the diagnoses.⁽²⁷⁾

...

A second HDACi, romidepsin, is an intravenously administered bicyclic peptide that inhibits classes I and II HDACs with activity in not only CTCL, but also peripheral T-cell lymphoma (PTCL). A single-arm, open-label, multicenter, pivotal, phase 2 study of romidepsin for the treatment of refractory CTCL (stages IB–IVA) was recently completed. After 6 cycles of

treatment, a response rate (RR) of **34%** was observed in **96** evaluable patients (including 6 clinical CRs), and pruritus improved in **43%**. Median time to response was **2** months. Romidepsin was granted approval by the FDA for treatment of patients with CTCL.⁽²¹⁾

Chemotherapy is reserved for relapsed and refractory disease and yields moderate to high response rates; however, response durations are short. Agents with notable activity include gemcitabine and liposomal doxorubicin. In a phase 2 study, gemcitabine showed a response rate of 53% and a CR rate of 22%. In a retrospective analysis of pegylated liposomal doxorubicin, the response rate was **88%** (30 out of 34 patients) and approximately 43% had CR.^(22, 34, 35)

5.11.2 Laboratory Data	
5.11.3 Electrocardiograms	28
5.11.4 Vital Signs	28
5.11.5 Eastern Cooperative Oncology Group Performance Status	28
5.11.6 Other Safety Assessments	28
6. CHANGES TO PLANNED ANALYSES FROM PROTOCOL	28
7. PROGRAMMING CONSIDERATIONS	29
7.1 Statistical Software	29
7.2 Rules and Definitions	29
8. REFERENCES	29

List of Abbreviations and Definitions of Terms

Abbreviation	Term
ADC	antibody-drug conjugate
AE	adverse event
AIC	Akaike information criterion
ALCL	anaplastic large cell lymphoma
ALK	anaplastic lymphoma kinase
ALP	alkaline phosphatase
ALT	alanine aminotransferase
ANC	absolute neutrophil count
ANCOVA	analysis of covariance
AST	aspartate aminotransferase
ATA	antitherapeutic antibodies
ATC	anatomical therapeutic chemical
BIC	Bayesian information criterion
BSA	body surface area
BUN	blood urea nitrogen
BV	brentuximab vedotin
CD30+	CD30-positive
CDF	cumulative distribution function
CI	confidence interval
C_{max}	maximum plasma concentration
C_{min}	minimum plasma concentration
CO_2	carbon dioxide
CR	complete response
CT	computed tomography
CTCL	cutaneous T-cell lymphoma
C_{trough}	trough concentration
CV	coefficient of variation
DOR	duration of response
ECOG	Eastern Cooperative Oncology Group
eCRF	electronic case report form
EFS	event-free survival
EOT	end of treatment
GGT	gamma-glutamyl transpeptidase
GRS	global response score
HDL	high-density lipoprotein
HLT	High Level Term
IDMC	independent data monitoring committee
IRF	independent review facility

Abbreviation	Term
ITT	intent-to-treat
IV	intravenous; intravenously
IVRS	interactive voice response system
LDH	lactic dehydrogenase
LDL	low density lipoprotein
MedDRA	Medical Dictionary for Regulatory Activities
MF	mycosis fungoides
MID	minimum important difference
MMAE	monomethylauristatin E
MRU	medical resource utilization
mSWAT	modified severity weighted assessment tool
MTX	methotrexate
NCI CTCAE	National Cancer Institute Common Terminology Criteria for Adverse Events
ORR	objective response rate
ORR4	objective response lasting at least 4 months
pcALCL	primary cutaneous anaplastic large cell lymphoma
PD	progressive disease (disease progression)
PFS	progression-free survival
PK	pharmacokinetic(s)
PP	per protocol
PR	partial response
PRO	patient-reported outcome
PT	Preferred Term
SAE	serious adverse event
SAP	statistical analysis plan
sCD30	soluble CD30
SOC	System Organ Class
SOE	Schedule of Events
T3	triiodothyronine
T4	thyroxine
TEAE	treatment-emergent adverse event
TSH	thyroid-stimulating hormone
WHO	World Health Organization

1. INTRODUCTION

In general, the purpose of the Statistical Analysis Plan (SAP) is to provide a framework that addresses the protocol objectives in a statistically rigorous fashion, with minimized bias or analytical deficiencies. Specifically, this plan has the following purpose:

To prospectively (a priori) outline the types of analyses and data presentations that addresses the study objectives outlined in the protocol, and to explain in detail how the data will be handled and analyzed, adhering to commonly accepted standards and practices of biostatistical analysis in the pharmaceutical industry.

1.1 Study Design

This is an open-label, randomized, multicenter study. All patients must have histologically-confirmed CD30-positive (CD30+) cutaneous T-cell lymphoma (CTCL) by central laboratory assessment and pathology review. Patients are to be stratified by diagnosis: primary cutaneous anaplastic large cell lymphoma (pcALCL) or mycosis fungoides (MF), and randomized to treatment with brentuximab vedotin monotherapy (Arm 1) up to 16 cycles total (48 weeks), or methotrexate (MTX) or bexarotene per physician's choice (Arm 2) up to a total of 48 weeks.

Objective response, lasting at least 4 months (ORR4), per independent review facility (IRF) will be assessed by global response score (GRS), which consists of skin evaluation (mSWAT assessment), nodal and visceral radiographic assessment, and detection of circulating Sézary cells (MF only). Complete response (CR) or partial response (PR) per GRS will be confirmed by sustained response in skin per mSWAT assessment at the subsequent cycle. All randomized patients will be followed for survival every 12 weeks for a minimum of 24 months after the EOT visit, and then every 6 months until patient withdrawal, death, or study closure.

Patients with a documented PR or CR at the end of Cycle 3 and at any disease assessment thereafter may continue treatment with study drug for up to 16 cycles with brentuximab vedotin or 48 weeks with bexarotene or methotrexate; patients with stable disease may continue therapy at the discretion of the investigator. Patients with progressive disease (PD) at any time during the study will be discontinued from study treatment. Patients with increasing mSWAT before assessment at the end of Cycle 3 will be allowed to continue therapy until the Cycle 3 assessment if, in the investigator's opinion, the findings are due to tumor flare rather than disease progression.

1.2 Study Objectives

1.2.1 Primary Objectives

The primary objective is:

• To determine ORR, lasting at least 4 months, with brentuximab vedotin in patients with CD30+ MF or pcALCL compared to that achieved with therapy in the control arm

1.2.2 Secondary Objectives

The key secondary objectives are:

- To determine complete response (CR) rate with brentuximab vedotin compared to that achieved with therapy in the control arm
- To determine progression-free survival (PFS) with brentuximab vedotin compared to that achieved with therapy in the control arm
- To determine burden of symptoms during treatment with brentuximab vedotin compared to that achieved with therapy in the control arm

Other secondary objectives include:

- To assess duration of response (DOR) with brentuximab vedotin
- To assess duration of skin response with brentuximab vedotin
- To determine event-free survival (EFS) with brentuximab vedotin compared to that achieved with therapy in the control arm
- To describe the pharmacokinetics (PK) of brentuximab vedotin and monomethylauristatin E (MMAE) in blood
- To determine the immunogenicity of brentuximab vedotin
- To assess patient-reported quality of life outcomes
- To assess the safety of brentuximab vedotin

1.2.3 Exploratory Objectives

The exploratory objectives include:

2. POPULATIONS FOR ANALYSIS

2.1 Intent-to-Treat Population

The Intent-to-Treat (ITT) population will include all patients identified as CD30+ by the Ventana CD30 (Ber-H2) assay and randomized to treatment. All patients in the ITT population will be analyzed according to the treatment they were randomized to receive and not according to what they actually received, if different.

The ITT population will be used for the primary efficacy analysis and analyses on all efficacy endpoints unless specified otherwise.

2.2 All-Enrolled Population

The All-Enrolled population will include all patients randomized to treatment. All patients in the All-Enrolled population will be analyzed according to the treatment they were randomized to receive and not according to what they actually received, if different.

The all-enrolled population will be used as a supplement to the analysis of the ITT population for the primary efficacy endpoint.

2.3 Per-Protocol Population

The Per-Protocol (PP) population will include a subset of ITT patients who do not have major protocol violations as determined by the medical monitor. All decisions to exclude patients from the PP population will be made before the study database lock.

The PP population will be used as a supplement to the analysis of the ITT population for the primary efficacy endpoint.

All patients in the PP population will be analyzed according to the actual treatment received.

2.4 Response-Evaluable Population

The Response-Evaluable population is defined as a subset of the ITT population with measurable disease at baseline and with at least 1 post baseline response assessment. The Response-Evaluable population will be used for the sensitivity analyses of ORR4, CR rate, ORR, time to response, and duration of response, as needed.

2.5 Safety Population

The Safety population will include patients who receive at least 1 dose of study drug. All patients in the Safety population will be analyzed according to the actual treatment received. Patients receiving any dose of brentuximab vedotin will be grouped into the study drug group for the purposes of safety reporting.

All safety analyses will be performed using the Safety population.

2.6 Pharmacokinetics Population

The PK population will include patients with sufficient dosing and PK data to reliably estimate PK parameters as determined by a clinical pharmacologist.

PK analyses will be performed using the PK population.

2.7 Pharmacodynamics Population

The Pharmacodynamics population will include patients with sufficient dosing and sufficient pharmacodynamics data to reliably measure pharmacodynamics parameters.

Pharmacodynamic analyses will be performed using the Pharmacodynamics population.

3. HYPOTHESES AND DECISION RULES

3.1 Statistical Hypotheses

The primary null hypothesis to be tested is that the proportion of patients achieving ORR4 per IRF is not different between the brentuximab vedotin (BV) treatment group and the physician's choice treatment group (MTX or bexarotene); i.e.,

$$H_0$$
: $ORR4_{BV} = ORR4_{Control}$

The alternative hypothesis is that ORR4 per IRF in the brentuximab vedotin treatment group is higher than that of the physician's choice group, i.e.,

$$H_A$$
: $ORR4_{BV} > ORR4_{Control}$

The key secondary hypotheses to be tested include:

- CR rate per IRF is not different between the brentuximab vedotin treatment group and the physician's choice treatment group.
- PFS is not different between the brentuximab vedotin treatment group and the physician's choice treatment group.
- Changes in symptom domain per the Skindex-29 assessment tool are not different between the brentuximab vedotin treatment group and the physician's choice treatment group.

3.2 Statistical Decision Rules

The primary null hypothesis will be tested at a type I error rate of 0.05 (2 sided). We will conclude that brentuximab vedotin treatment can significantly improve the ORR4 compared to the physician's choice (MTX or bexarotene) in patients with CD30+ CTCL if the ORR4 for the brentuximab vedotin treatment group is statistically significantly higher than that of the physician's choice treatment group in the primary efficacy analysis (refer to Section 5.8.1.1).

A fixed sequential testing procedure will be used to test between the primary endpoint and the key secondary endpoints; that is, the key secondary endpoints will be tested only if the primary endpoint is statistically significant.

To test the key secondary endpoints, a weighted Holm procedure (1) will be used. The weighted Holm testing procedure is applied at the final analysis at the 0.05 level (2-sided) with weights: 0.7, 0.2, and 0.1 for CR, PFS, and the symptom domain of the Skindex-29, respectively. Once the unadjusted 2-sided p-values p_i , i = 1,2,3 are obtained for each endpoint, q-values q_i , i = 1,2,3 are calculated by dividing the p-values with their respective weights $q_i = \frac{p_i}{c_i}$, where c_i is the weight for endpoint i, i = 1,2,3. Then the ordered q-values, $q_{[1]} \le q_{[2]} \le q_{[3]}$, are compared with 0.05 divided by the sum of weights corresponding to that q-value and any larger q-values in a step-down fashion starting with the smallest q-value. Specifically, we identify the smallest i such that $q_{[i]} > \frac{0.05}{s}$, and claim significance $\sum_{i=1}^{3} c_{[i]}$

for endpoints corresponding to $q_{[1]},...,q_{[i-1]}$. If i=1, then no endpoint is significant, and if i does not exist, then all endpoints are significant.

Assuming that the probabilities of success for the endpoints are 0.85, 0.55, and 0.50 with a 0.05 (2-sided) individual alpha level and a multivariate normal distribution with an equal correlation of 0.5 among all endpoints, the power to detect at least 1 significant endpoint is 84%, and the powers to show significance for CR, PFS, and the symptom domain of the Skindex-29 using the weighted Holm method are 82%, 48%, and 40%, respectively.

The weighted Holm testing procedure controls the type I error unconditionally. The impact on power has been evaluated through simulation for a range of correlation and/or success probability assumptions. Holding the success probabilities as assumed, the power to detect at least 1 significant endpoint decreases from 89% to 81% when correlation between endpoints increases from 0.1 to 0.9. Holding the correlation as assumed, the power to detect at least 1 significant endpoint increases from 79% to 88% when probabilities of success for all 3 endpoints increases from 0.8, 0.5, and 0.45 to 0.9, 0.6, and 0.55, respectively.

Primary and key secondary endpoints are tested at the 0.05 level, and the key secondary endpoints are gated by the primary endpoint. Due to the sequential procedure property, the overall type I error rate for testing the primary and key secondary endpoints is strongly controlled at the 0.05 level.

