5.1 Sample Size Justification

Approximately 124 patients (approximately 62 patients per treatment arm) will be randomized to the study (124 patients are targeted for the ITT population). The sample size was calculated to provide 90% power to detect a 30% improvement in ORR4 in the brentuximab vedotin treatment group, assuming ORR4 for the MTX or bexarotene alone treatment group is 40%. This calculation is based on a 2-sided χ^2 test with a significance level of $\alpha = 0.05$, and a 10% dropout rate using nQuery Advisor 7.0. A minimum of 30 patients (15 per treatment arm) with pcALCL will be included in the study.

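### The key-secondary powers in SAP 3.2 describe the weighted Holm step alone; they omit the ORR4 gate without saying so, which overstates the power for CR and for at least one endpoint.

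*SAP*

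**What the plan says.** SAP 3.2 sets a two-stage procedure. ORR4 is tested first, at 0.05 two-sided, and "the key secondary endpoints will be tested only if the primary endpoint is statistically significant". SAP 5.8.2.1.2 and Protocol 8.1.6.2 repeat the gate. The three key secondaries then share 0.05 by weighted Holm, "with weights: 0.7, 0.2, and 0.1 for CR, PFS, and the symptom domain of the Skindex-29, respectively".

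The power statement in SAP 3.2 rests on three inputs besides the weights and the overall alpha:

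- "probabilities of success for the endpoints are 0.85, 0.55, and 0.50 with a 0.05 (2-sided) individual alpha level";
- "a multivariate normal distribution with an equal correlation of 0.5 among all endpoints";
- the Holm procedure itself.

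From these it concludes that "the power to detect at least 1 significant endpoint is 84%, and the powers to show significance for CR, PFS, and the symptom domain" are 82%, 48% and 40%. Two sensitivity statements follow. As the correlation rises from 0.1 to 0.9, "the power to detect at least 1 significant endpoint decreases from 89% to 81" percent. As the three success probabilities rise together, the same power goes from 79% to 88%.

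The power of ORR4 is given separately, in SAP 5.1: "The sample size was calculated to provide 90% power".

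**The concern.** Under the written procedure a key secondary can be claimed only if two things happen: ORR4 is significant and the Holm step rejects. The inputs listed for the power statement cover only the second. Neither the 90% power of ORR4 nor its correlation with the key secondaries appears, and no label says that the figures exclude the gate.

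A reader will take 84% and 82% as the chance that this trial supports at least one key-secondary claim, and a CR claim. If the gate was left out, those chances are overstated, by at most the 10% probability that the gate stays shut. The sensitivity ranges would have the same gap.

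**Working it through.** **Inputs from the documents.** Weights 0.7, 0.2, 0.1 and overall alpha 0.05 two-sided; success probabilities 0.85, 0.55, 0.50 at 0.05 two-sided; correlation 0.5 (all SAP 3.2). ORR4 power 90% (SAP 5.1).

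**Input not in the documents.** The correlation of ORR4 with each key secondary. It is varied below.

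**Model.** Each endpoint has a normal test statistic with mean z(success probability) + 1.960:

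- CR: 1.036 + 1.960 = 2.996
- PFS: 0.126 + 1.960 = 2.086
- Skindex-29: 0 + 1.960 = 1.960
- ORR4: 1.282 + 1.960 = 3.242

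The first Holm step uses 0.7 × 0.05 = 0.035 for CR, 0.2 × 0.05 = 0.01 for PFS and 0.1 × 0.05 = 0.005 for Skindex-29. Later steps follow SAP 3.2. Each scenario uses 2,000,000 draws, so simulation error is a few hundredths of a point.

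**Step 1: reproduce the plan, no gate.**

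| | At least one | CR | PFS | Skindex-29 |
|---|---|---|---|---|
| Stated in SAP 3.2 | 84% | 82% | 48% | 40% |
| Simulated, no gate | 83.5% | 81.7% | 48.1% | 40.5% |

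The sensitivity figures also reproduce without a gate, within about a point: 88.3% and 81.3% (stated 89% and 81%), and 78.2% and 88.7% (stated 79% and 88%).

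**Step 2: add the gate.** A key secondary now counts only if the ORR4 statistic also exceeds 1.960. ORR4 power is 90%; the correlation among the three secondaries stays at 0.5.

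| Correlation of ORR4 with the secondaries | At least one | CR | PFS | Skindex-29 |
|---|---|---|---|---|
| 0 with each | 75.1% | 73.5% | 43.3% | 36.4% |
| 0.5 with each | 78.2% | 76.6% | 46.8% | 39.6% |
| 0.8 with each | 81.2% | 79.4% | 48.1% | 40.4% |
| 0.9 with CR, 0.5 with the others | 81.8% | 80.6% | 47.3% | 40.1% |

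The first row can be checked by hand, since independence means multiplying by 0.90: 0.90 × 83.5 = 75.1 and 0.90 × 81.7 = 73.5.

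**Step 3: the sensitivity ranges with the gate.** If ORR4 shares the varied correlation, power for at least one endpoint is 79.9% at 0.1, 78.2% at 0.5 and 80.2% at 0.9. The stated fall from 89% to 81% becomes about 80% at both ends. With ORR4 correlation 0.5, the stated rise from 79% to 88% becomes 73.9% to 82.4%.

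**Step 4: are the stated figures powers given a significant ORR4?** Divide the gated figures at correlation 0.5 by 0.90: 78.2/0.90 = 86.9%, 76.6/0.90 = 85.1%, 46.8/0.90 = 52.0%, 39.6/0.90 = 44.0%. These are not 84/82/48/40. The two sets agree only if ORR4 is independent of the secondaries.

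**Step 5: ORR4 power above 90%.** The two-proportion calculation for 70% against 40% (Protocol 8.1.1) needs 56 per arm for 90% power, and about 62 allows for 10% dropout. If all 62 per arm contribute at those rates, ORR4 power is about 93%, and the gated figures at correlation 0.5 are about 80%, 78%, 47% and 40%.

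**The case against.** The best defence is that nothing is miscalculated. Each stated figure follows from its stated inputs, the individual powers are attributed to the weighted Holm method, and the gate is described in the same section. That stands: the defect is an incomplete and unlabelled statement, not faulty arithmetic.

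The second defence is that the size of the loss is unknown. This also stands in part. The 0.5 in SAP 3.2 belongs to the three Holm endpoints; applying it to ORR4 is an assumption of this check. ORR4 and CR both come from the IRF global response score (SAP 5.8.1 and 5.8.2), so a high correlation between them is plausible. At 0.9 the loss is only about 1 to 2 points. It does not vanish anywhere in the range examined.

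Third, no design decision in the documents is shown to rest on these figures. The sample size rests on ORR4 alone. That limits the weight of the point but does not make the figures those of the written procedure.

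A reader might infer more than the documents support:

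- *All four powers are materially wrong.* They are not. PFS and Skindex-29 change by about a point or less at correlation 0.5, and fall to about 43% and 36% only if ORR4 is nearly uncorrelated with them.
- *Error control or the size of the trial is compromised.* Neither depends on this power statement.
- *The figures are simply powers conditional on a significant ORR4.* Step 4 shows that this holds only under independence, which is hard to defend when ORR4 and CR share an assessment.

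**Conclusion.** The point holds for two of the four figures. The stated powers are those of the weighted Holm step alone. Under the full procedure, with ORR4 power of 90% and an assumed correlation of 0.5, at least one endpoint is about 78% against a stated 84%, and CR about 77% against 82%: a loss of 5 to 6 points. Across the correlations examined, measured against the reproduced 83.5% and 81.7%, the loss runs from about 8 points at correlation 0 to about 1 to 2 points at an ORR4-CR correlation of 0.9.

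The correlation sensitivity statement changes in kind as well as level. The reported decline with rising correlation largely disappears once ORR4 gates the family and shares that correlation.

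That the gate is omitted is firm, because every stated figure reproduces without it. The exact size of the overstatement is not firm, because the correlation of ORR4 with the secondaries is not in the documents.

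**What to change.** In SAP 3.2:

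1. Rerun the simulation with ORR4 as a fourth variable that must be significant before any key secondary counts.
2. State the ORR4 power and the ORR4-to-secondary correlations assumed, with a higher ORR4-CR correlation among the scenarios.
3. Report the gated powers and both gated sensitivity ranges, showing how they vary with the assumed correlation.
4. If the present figures stay beside them, label them *weighted Holm step only, primary gate not included*. Do not label them *conditional on a significant primary endpoint*; at correlation 0.5 those powers would be about 87%, 85%, 52% and 44%.

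The cost is one rerun of an existing simulation and a few lines of text. The stated powers for CR and for at least one endpoint become less favourable. No test, weight, alpha level or sample size changes.
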